2 STUDY OBJECTIVES & OUTCOMES

Table 1: Primary Objectives and Outcome Measures

Primary Objective	Outcome Measure	Timepoints measured
To determine the effect of EC-nicotine free on vascular function as compare to TC.	Change in FMD between the TC group and the EC-nicotine free groups	0 and 4 weeks

Table 2: Secondary Objectives and Outcome Measures

[figure not shown]
Secondary Objectives	Outcome Measures	Timepoints measured
To compare the effects of EC-nicotine vs EC-nicotine free on vascular function.	Change in FMD between EC-nicotine and EC-nicotine free groups	0 and 4 weeks
To compare the effects of EC-nicotine free vs TC on vascular function.	Change in Pulse Wave Velocity between the TC group and the EC-nicotine free groups. Change in Augmentation Index@75bpm between the TC group and the EC-nicotine free groups	0 and 4 weeks
To compare the effects of TC vs EC vs EC nicotine free on oxidative stress.	Change in total F2-Isoprostanes between the TC and EC groups	0 and 4 weeks

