4.2 SECONDARY OUTCOMES

- Change in FMD between EC-nicotine and EC-nicotine free groups
- Change in Pulse Wave Velocity between the TC group, EC-nicotine and the EC-nicotine free groups
- Change in Augmentation Index@75bpm between the TC group, EC-nicotine and the EC-nicotine free groups
- Change in oxidised LDL, hs-CRP, tPA and PAI-1 between the TC, EC-nicotine free and EC-nicotine groups

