5 STATISTICS AND DATA ANALYSIS

5.1 SAMPLE SIZE CALCULATION

The primary endpoint measurement is change in brachial artery FMD, which is expressed as the maximum FMD percentage change from baseline. Based on our existing data for this measure (mean response 7.8%, SD=3.5%), and assuming mean FMD reductions of 2%, 1% and 0% in the EC-Nicotine-free, EC-Nicotine, and TC groups respectively with a SD of the change in FMD =3.0% (based on our previous study[1]), and a using a sample size calculation using Linear Contrast Tests[2] a sample size of 36 subjects in each group will have 80% power to detect an improvement in FMD of 2.0% and 1.0% in the EC-nicotine-free and EC-nicotine groups respectively compared to the TC group at 5% significance. Assuming 10%, 15%, and 20% drop-out rates in the TC, EC-nicotine & EC-nicotine-free groups respectively, we will require 135 completed subjects. All drop-outs will be replaced to achieve 36 completed subjects in each group to fulfil the explanatory nature of the trial.

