5.2 STATISTICAL ANALYSES

Descriptive statistics in the form of means and standard deviations for continuous variables and percentages and denominators for categorical variables will be tabulated for baseline and at the 4 week visit. The dependent variable will be assessed for approximation to a normal distribution and transformed if necessary. Pre-specified subgroup analyses will be completed by fitting the appropriate interaction term in the regression model and if significant outcomes will be presented separately by level of subgroup. All comparisons will be between treatment groups (EC-nicotine vs EC-nicotine free vs TC) at the final visit (4 weeks), adjusted for the baseline measure of the outcome.

The statistical analysis will be carried out in accordance to TASC SOP 57 "The implementation of statistical analysis in clinical research" by the study team statistician.

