8.1 SECONDARY ANALYSES

- 1) Changes in Oxidised LDL between baseline and Visit 4
- 2) Changes in High-sensitivity CRP between baseline and Visit 4
- 3) Changes in Tissue Plasminogen Activator between baseline and Visit 4
- 4) Changes in Platelet Activation Inhibitor-1 (PAI-1) between baseline and Visit 4

Subgroup analyses: interaction terms of treatment in men vs women, upper tertile baseline smoking versus lower tertile comparisons for all primary and secondary endpoints All secondary outcomes will be analysed in the same manner as the primary outcome. Results will be presented as between group differences in measured parameters between the baseline and final visit.

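### The SAP widens PWV and AIx@75 to three arms, replaces one oxidative-stress marker with four blood markers, and tests every secondary like the primary with no order, adjustment or exploratory label

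*SAP*

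**What the plan says.** **Protocol, section 2, Table 2.** Secondary FMD is compared between the two e-cigarette arms. For arterial stiffness the outcome is "Change in Pulse Wave Velocity between the TC group and the EC-nicotine free groups", and AIx@75 has the same single pair. The oxidative-stress objective covers TC, EC and EC-nicotine free, measured by total F2-isoprostanes. The protocol Summary also describes oxidative stress as a comparison of all three groups.

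**SAP 4.2.** Secondary FMD is unchanged. The PWV entry becomes "Change in Pulse Wave Velocity between the TC group, EC-nicotine and the EC-nicotine free groups", and AIx@75 is widened in the same way. F2-isoprostanes no longer appear. Oxidised LDL, hs-CRP, tPA and PAI-1 are listed across three arms.

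**SAP 5.2.** "All comparisons will be between treatment groups (EC-nicotine vs EC-nicotine free vs TC) at the final visit (4 weeks"), adjusted for the baseline value.

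**SAP 8 and 8.1.** The primary analysis is a linear contrast test plus a multiple regression with experimental group. For the rest: "All secondary outcomes will be analysed in the same manner as the primary outcome". SAP 8.1 also adds two subgroup interactions (sex, and upper against lower tertile of baseline smoking) for every primary and secondary endpoint.

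The only significance level in either document is in the FMD sample-size text, "compared to the TC group at 5% significance" (SAP 5.1, with matching text in Protocol 8.1 and the protocol Summary). No level, order, adjustment or exploratory status is given for the secondaries.

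**The concern.** The protocol named in advance which pair of arms would decide PWV and AIx@75. The SAP removes that choice and does not say which contrast now decides. A nominally significant result on a pair that the protocol never named could therefore be reported with the same standing as the planned one. The added blood markers multiply these opportunities.

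Status matters here because the TC arm is not randomised (Protocol 5.5.1): participants choose between continuing to smoke and entering the randomisation. EC-nicotine against EC-nicotine free is the only randomised comparison, and on FMD it is one secondary among several. Of the three possible pairs for any other outcome, two involve the self-selected arm. A chance TC difference in stiffness, inflammation or fibrinolysis would carry the same formal weight as the randomised FMD result. The sample size was worked out for FMD only.

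**Working it through.** **1. The plan's own figure.** Inputs from SAP 5.1: "assuming mean FMD reductions of 2%, 1% and 0% in the EC-Nicotine-free, EC-Nicotine, and TC groups respectively" (only the sizes are used here), "with a SD of the change in FMD =3.0" (per cent), 36 per group, 80% power, 5%. With weights (−1, 0, 1) for TC, EC-nicotine and EC-nicotine free, the linear contrast reduces to EC-nicotine free against TC, a difference of 2.

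- Standard error = 3 × √(2/36) = 0.707, and 2 / 0.707 = 2.83.
- Two-sided n = 2 × (1.96 + 0.84)² × 3² / 2² ≈ 35.3, so 36. One-sided would need 28.
- Power at 36 per group: Φ(2.83 − 1.96) ≈ 0.807. With a noncentral t on 105 df it is 0.800.

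The stated 36 is reproduced at two-sided 5%, so two-sided 5% is assumed for each secondary test below.

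**2. How many tests?** SAP 4.2 has seven secondary outcomes: FMD (one named pair) and six three-arm outcomes (PWV, AIx@75, oxidised LDL, hs-CRP, tPA, PAI-1). The SAP does not fix the number of contrasts, so three readings are shown:

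- one test per outcome, such as the linear contrast alone: 1 + 6 × 1 = 7
- each e-cigarette arm against TC: 1 + 6 × 2 = 13
- all pairs: 1 + 6 × 3 = 19

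Protocol Table 2 gives 4 tests with one per outcome. It gives 3 + 3 = 6 if its three-arm oxidative-stress objective is tested on all pairs.

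**3. Chance of at least one false positive.** If tests were independent, 1 − 0.95^k would give 18.5% (k = 4), 30.2% (7), 48.7% (13) and 62.3% (19). Contrasts that share an arm are not independent, and outcomes may be correlated. The table therefore comes from simulating three equal arms with no true effects and a common correlation ρ between outcomes. The documents give no correlations, so ρ is an assumption.

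| Family | ρ = 0 | ρ = 0.5 | ρ = 0.8 |
|---|---|---|---|
| Protocol, 4 tests | 19% | 17% | 14% |
| Protocol, 6 tests | 25% | 22% | 18% |
| SAP, 7 tests | 30% | 24% | 17% |
| SAP, 13 tests | 46% | 37% | 26% |
| SAP, 19 tests | 57% | 45% | 31% |

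Repeating the 7-, 13- and 19-test families with t-tests on 36 per arm (105 df), at ρ = 0 and 0.8, agrees to within a percentage point. The expected number of false positives does not depend on ρ: 7 × 0.05 = 0.35, 13 × 0.05 = 0.65, 19 × 0.05 = 0.95. Subgroup interactions are excluded and would add further tests.

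**4. Power of the randomised FMD comparison.** The planning means differ by 2 − 1 = 1. Then 1 / 0.707 = 1.414, and power ≈ Φ(1.414 − 1.96) = Φ(−0.546) ≈ 29%, before any gain from baseline adjustment.

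**The case against.** The strongest case on the other side is that the SAP never asks for all pairwise comparisons. Its rule is to treat secondaries like the primary, and the primary method starts with one linear contrast. On that reading there are 7 tests, not 19. The outcomes are labelled secondary, the protocol (section 1.1) describes the study as preliminary, and the FMD comparison between the e-cigarette arms is already listed first. The three-decimal p-values in SAP 9 are a formatting rule and claim nothing.

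Much of this stands. It rules out several stronger readings that a reader might infer:

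- **That every secondary was widened from one contrast to three.** Only PWV and AIx@75 were. Secondary FMD is the same single pair in both documents, and oxidative stress was already three-arm in the protocol. Table 2 names none of the four blood markers, so their growth comes from replacing one marker with four.
- **That a false-positive secondary is close to even odds.** This needs 13 or 19 tests and low to moderate correlation. The SAP specifies neither.
- **That the error rate is many times a stated 5%.** The 5% belongs to the FMD sample size. It was never set as a family-wise limit for the secondaries, and testing each at full 5% is inferred from silence.

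The objection does not remove the defect. The primary method also includes a regression on a three-level group, which gives at least two contrasts if group is coded as categorical, and SAP 5.2 describes every comparison as three-arm. If the number of contrasts cannot be read from the plan, the deciding contrast can be chosen after the data are seen. The preliminary stance is a reason to label these results exploratory, which neither document does.

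**Conclusion.** The point holds in a limited form. The SAP departs from Protocol Table 2 on PWV and AIx@75, exchanges one oxidative-stress marker for four blood markers, and leaves the number, order and status of the secondary tests undefined. With no true effects and each test at an assumed two-sided 5%, the chance of at least one false-positive secondary is about 17–30% for 7 tests and 31–57% for 19, for correlations of 0.8 to 0. The range is wide because the plan does not fix the number of contrasts and gives no correlations. The protocol's own list would give about 14–25%, so the SAP enlarges an existing gap and did not create all of it.

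This does not affect the primary FMD test or its sample size. It affects which secondary results can be believed and how they may be described. It should be corrected, but it does not threaten the trial.

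**What to change.** Amend SAP 4.2 and 8.1 before database lock:

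1. Restore TC against EC-nicotine free as the named comparison for PWV and AIx@75, as in Protocol Table 2.
2. Keep EC-nicotine against EC-nicotine free on FMD first among the secondaries, and identify it as the only randomised FMD comparison. State its power: about 29% for a 1% difference (SD 3%, 36 per arm, before baseline adjustment). A null result there would then not be read as evidence of no nicotine effect.
3. Keep the three-arm oxidative-stress objective as a protocol secondary, and reconcile which marker serves it, F2-isoprostanes or oxidised LDL. Protocol section 6 lists oxidised LDL among the blood tests but not F2-isoprostanes, so the protocol needs the same check.
4. Report hs-CRP, tPA, PAI-1 and every arm pair not named in the protocol as exploratory: estimates with 95% confidence intervals, stated to be unadjusted for multiplicity and not used to claim an effect.

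The cost is a few lines of text, with no extra participants or analyses. The downside is that a nominally significant result on those markers or arm pairs can be reported only as exploratory. The labels do not lower any error rate: the named secondaries that remain are 4 to 6 tests, with about a 14–25% chance of a false positive. If the sponsor wants to claim effects on secondaries, an explicit adjustment is needed. Bonferroni thresholds would be 0.05/7 = 0.0071 for 7 tests and 0.05/19 = 0.0026 for 19.

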8.2 TREATMENT ADHERENCE

We will measure Carbon Monoxide (CO) levels as a recent paper (Yan et al. Regul Toxicol Pharmacol. 2015 Feb;71(1):24-34) has shown that ECs do not affect CO levels.

CO breath test will be measured as an indicator of treatment allocation adherence and will be added to the primary model to assess the effect of adherence.

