5.5 RANDOMISATION

5.5.1 Randomisation

Randomisation will be carried out in a 1:1 fashion for the 2 randomised arms via a centrally controlled web-based GCP compliant randomisation system, TRUsT, run by Tayside Clinical Trials Unit (TCTU). To ensure balanced assignment across critical variables, a minimisation algorithm will be employed, using baseline age (≤ 40 years; > 40 years), sex (male; female) and smoking pack years (≤ 20 pack years; > 20 pack years). Randomisation will be performed by the PI, researcher or other local delegated individual.

Recruitment will stop when the required number is reached in each arm (maximum 45 per arm)

The TC arm will not be randomised.

To facilitate recruitment and minimise dropouts we propose to recruit the TC smoking arm as a separate non randomised group. Potential participants will be identified and approached in exactly the same ways as for the 2 EC arms. All participants will be asked if they wish to continue to smoke TC or to be randomised to one of the EC arms. This will enable us to recruit volunteers who would find it too difficult to stop their TC for 4 weeks. It will also avoid disappointment for those volunteers who are ready to stop smoking and do not wish to continue with their TC, which has the potential to lead to further dropouts. This is an unblinded study with the exception of the measurement of endothelial function and vascular stiffness which will be performed by a single blinded operator.

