5.5.2 Intervention Allocation

Participants will initially be asked if they wish to continue smoking TC or if they would like to be randomised to one of the EC arms. Participants who wish to be randomised to one of the EC arms will be randomised to one of two groups in a 1:1 fashion. The groups will be:

- a) Switch to electronic cigarettes containing nicotine plus flavour
- b) Switch to electronic cigarettes containing flavour alone

Participants wishing to join the TC arm will be asked to continue their usual daily smoking habits, however, they will be asked not to smoke more than 30 cigarettes per day. Participants in this group will be asked not to use electronic cigarettes for the four week period of the trial.

For the groups receiving the electronic cigarettes, the Researcher or delegated individual will “dispense” the electronic cigarettes to participants. Instructions and explanation of how to use the electronic cigarettes will be given. Participants will be asked not to smoke tobacco cigarettes during the trial period.

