6.2 ANALYSIS POPULATIONS

The primary analysis will be based on the evaluable dataset in an explanatory trial and so is a per-protocol population. A secondary intention-to-treat analysis will also be implemented.

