8 PRIMARY ANALYSIS

The FMD response relationship will be assessed by a linear contrast test, and a multiple linear regression on FMD at 4 weeks including the baseline FMD level and experimental group as covariates. The model will also include the minimisation variables; baseline age (≤40 years; >40 years), sex (male; female) and smoking pack years (≤20 pack years; >20 pack years).

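### Breath CO added to the three-arm model (SAP 8.2) does not estimate an effect of adherence, and the CO-adjusted TC coefficient is not the overall between-group difference

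*SAP*

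**What the plan says.** SAP 8 defines the primary analysis as a linear contrast test and a regression of week-4 FMD on baseline FMD and experimental group. It then adds "The model will also include the minimisation variables". CO is not among the terms.

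SAP 8.2 treats the CO breath test as the indicator of adherence to allocation and says that it "will be added to the primary model to assess the effect of adherence". The reason given is that a published paper "has shown that ECs do not affect CO levels". The section does not state the visit, the coding, a CO-by-arm term, a restriction to the EC arms, or how the coefficients are to be read.

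The study matrix (Protocol 3.3) schedules the CO test at baseline and week 4, and an adherence item at week 4 only.

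Protocol 5.5.2 gives the arms opposite instructions. For the EC arms: "Participants will be asked not to smoke tobacco cigarettes during the trial period". TC participants continue their usual smoking, and "Participants in this group will be asked not to use electronic cigarettes for the four week period of the trial".

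Protocol 6 asks EC-arm participants to abstain from smoking for 4 hours before visits and does not ask this of TC participants.

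The primary population is "based on the evaluable dataset in an explanatory trial and so is a per-protocol population", but neither SAP 5.3 nor SAP 6.2 gives an adherence criterion.

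**The concern.** A covariate can carry an adherence effect only if it measures adherence in the same sense for everyone who contributes to its slope. Here a high reading marks failure to follow the allocation in two arms and compliance with it in the third. One TC instruction, to avoid ECs, is invisible to CO on the SAP's own statement. The arms also follow different pre-visit smoking rules, so part of the CO gap may reflect time since the last cigarette.

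Week-4 CO is also measured after allocation and marks the tobacco exposure that switching is meant to change. Adjusting for it removes from the TC versus EC coefficient whatever part of the effect runs through that exposure.

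What is at stake is the interpretation of the only adherence analysis in the SAP. The slope could be reported as an effect of adherence when part of it reflects how heavily TC participants smoke. A small CO-adjusted TC difference could be reported as no effect once adherence is considered.

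**Working it through.** **Inputs from SAP 5.1.** 36 per arm; SD of change in FMD 3.0; assumed effects 0, 1 and 2 points (TC, EC-nicotine, EC-nicotine-free); 5% significance, taken as two-sided.

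**The plan's own figure.** For the contrast (-1, 0, 1), SE = 3.0 × √(2/36) = 0.707 and the noncentrality is 2.0/0.707 = 2.83. With 105 degrees of freedom, power is 0.800. The 36 per group reproduces. The plan states no figure for the CO analysis.

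**What the common slope estimates.** With arm indicators in the model and equal arm sizes, least squares gives

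b = (V_TC·b_TC + V_N·b_N + V_F·b_F) / (V_TC + V_N + V_F),

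where V is the within-arm variance of CO and b the within-arm slope (N = EC-nicotine, F = EC-nicotine-free). Baseline FMD and the minimisation variables are left out for simplicity. If CO relates to FMD only in the EC arms (b_TC = 0), and both EC arms have slope b_EC and variance v, then

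b / b_EC = 2v / (V_TC + 2v).

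With a proportion p of EC participants still smoking,

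v = (1 − p)·s_A² + p·s_S² + p(1 − p)·(m_S − m_A)²,

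where A is abstinent and S still smoking.

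**Assumed CO values (none are in the documents).** Abstinent EC: 3.5 ppm, SD 1.5.

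- Scenario 1: EC smokers 18 ppm, SD 6; TC SD 6.
- Scenario 2: EC smokers 12 ppm, SD 5; TC SD 6. The lower level allows for the 4-hour abstention.
- Scenario 3: as scenario 2, with TC SD 10.

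Example, scenario 1, p = 0.1: v = 0.9 × 2.25 + 0.1 × 36 + 0.09 × 14.5² = 2.03 + 3.60 + 18.92 = 24.55, and the ratio is 49.10/(36 + 49.10) = 0.58.

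Example, scenario 3, p = 0.1: v = 2.03 + 2.50 + 0.09 × 8.5² = 11.03, and the ratio is 22.06/(100 + 22.06) = 0.18.

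| Share of EC slope recovered | p = 10% | p = 20% | p = 30% |
|---|---|---|---|
| Scenario 1 | 58% | 70% | 76% |
| Scenario 2 | 38% | 50% | 57% |
| Scenario 3 | 18% | 27% | 33% |

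A simulation (36 per arm, 3,000 trials per scenario) used other assumed values: TC mean 15 to 25 ppm with SD 8 to 10, abstinent EC 4 (SD 2), smoking EC 12 (SD 5), and 10 or 30% smoking. With benefit only in EC participants who abstain, the pooled slope was −0.18 to −0.47 per 10 ppm, against −0.88 to −1.10 in the EC arms alone. Scenario by scenario, that is a recovery of 19 to 44%, inside the range above.

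**Why the population matters.** If EC participants who smoke are excluded (p = 0), v = 2.25. The ratio is then 4.5/(36 + 4.5) = 0.11 with TC SD 6. TC supplies the other 89% of the CO variation, and hardly any adherence variation is left to study.

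**What the adjusted TC coefficient estimates.** In the same simplified model,

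adjusted difference = (mean FMD_F − mean FMD_TC) − b·(mean CO_F − mean CO_TC).

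If the overall difference is 2.0 and a share s is carried by CO, this equals 2.0 × (1 − s): 2.0 at s = 0, 1.0 at s = 0.5 and 0 at s = 1. In the simulation with the whole effect carried by CO, the estimate was 1.58 to 1.93 without CO and about 0 with it. The adjusted figure depends on mechanism, not on how well participants adhered.

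**The case against.** The strongest reply is that no planned primary result changes. SAP 8 specifies its model without CO, SAP 8.2 reads most naturally as an additional model, and neither document says that the CO-adjusted group coefficient will be reported as the treatment effect. This stands, and it confines the problem to the adherence analysis.

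Second, SAP 8.2 does not prescribe a common linear slope. Coding each participant as adherent or not to the allocated arm would remove the reversal of meaning. That is fair: the common slope is the natural reading, not stated text. But the SAP gives no such coding, and CO could not supply the part of it that concerns EC use in TC. The visit is less open than it looks, because the adherence item in the matrix is at week 4 only.

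Three stronger readings are tempting, and the documents do not support them.

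- A reader might infer that power for the main comparison falls. A wider standard error would apply to a test of the group coefficient in the CO model, and the SAP plans no such test.
- A reader might infer from "Assuming 10%, 15%, and 20% drop-out rates in the TC, EC-nicotine & EC-nicotine-free groups respectively" that tobacco use will differ between the EC arms and distort their comparison. Drop-out is not continued smoking among completers, and drop-outs are to be replaced. A shift when smoking is unequal is also what an adherence adjustment is meant to produce.
- A reader might infer that the model spoils an otherwise randomised comparison with tobacco. It does not, because "The TC arm will not be randomised". That limitation exists with or without CO.

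**Conclusion.** The point holds for SAP 8.2 and should be corrected before outcome data are analysed. Followed on its natural reading, the section yields a CO slope that is not an effect of adherence, and a TC versus EC coefficient that is a difference at equal post-allocation tobacco exposure. That conclusion follows from the arm instructions and from the SAP's own statement about ECs and CO. It does not depend on any CO value.

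The size does depend on such values. With 10 to 30% of EC participants still smoking and no CO–FMD relation within TC, the common slope recovers roughly 18 to 76% of the EC slope across the assumed means and SDs. The range is an illustration, not a prediction.

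It would be wrong to conclude that the primary FMD estimate is biased or underpowered because of SAP 8.2. That estimate comes from SAP 8, which has no CO term.

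**What to change.** 1. State in SAP 8 and 8.2 that the between-group estimate comes from the SAP 8 model without post-baseline CO.
2. Replace the three-arm CO covariate with a supportive analysis of week-4 CO within the two randomised EC arms. Run it in all randomised EC participants with week-4 data, not in the per-protocol set, since excluding those who smoke would leave little to estimate. Fix the coding of CO before outcome data are analysed. A CO-by-arm term that reports only the EC-arm slopes is an acceptable alternative. Describe the result as concerning tobacco abstinence, because CO says nothing about use of the allocated EC liquid.
3. Describe week-4 CO by arm. Do not interpret any CO-adjusted TC versus EC coefficient as the treatment effect or as adherence-adjusted.

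The smoking diary should not be named as the check on EC use in TC unless it is shown to record it; the documents do not say that it does.

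The cost is SAP wording and one extra analysis of data already scheduled. The analysis would be small, and adherence is not randomised, so it stays exploratory. Assume that 10, 20 or 30% of 72 EC participants (2 × 36) still smoke, giving about 7 v 65, 14 v 58 or 22 v 50. With SE = 3.0 × √(1/n₁ + 1/n₂) = 1.19, 0.89 or 0.77 and 69 degrees of freedom, power for a 2-point adherent versus non-adherent difference is about 38, 60 or 73%.
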